This research addresses the following "big-picture" questions: "Is the density notification law recently adopted in AZ having the intended impact on patients receiving mammography at a Federally Qualified Health Center (FQHC)?" and "Are there positive or negative unintended consequences to this legislation?" We hypothesize that sending standard-language (as determined by legislators) notification about breast density along with a woman's mammogram results is a sub-optimal method of notification. Further, we hypothesize that the goals of educating women about their breast density, (including the impact that dense breast tissue can have on mammogram sensitivity and overall risk of breast cancer) and encouraging a discussion with their health care provider about breast cancer screening options, may not be achieved by sending written notification in the absence of additional efforts to educate women about breast density. We propose to answer these questions by conducting a 3-arm randomized trial. All arms will receive the standard density notification letter, but 2 arms will also receive educationally-enhanced notification about breast density. Thus, the 3 study arms are:

usual care (standard density notification only), enhanced (standard density notification + written educational materials on breast density), and interpersonal (standard density notification + written educational materials on breast density + verbal interaction with a *promotora*/health educator).

The impact of this research can only increase as additional states mandate that women attending mammography screening (many of whom have never heard of breast density before) receive written notification about their breast density and its role in breast cancer risk. Particularly in FQHC's and other community settings where breast imaging experts may not be on staff and patients may have limited English proficiency, lower health literacy, and fewer economic resources, it is critical that density notification occur in ways that optimize receptivity and comprehension, minimize anxiety and worry, and enhance self-efficacy and intention to continue screening and pursue supplemental breast screening, if appropriate.

Aims, purpose, or objectives:

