Follow-up (T4) Assessment. We will identify women enrolled in LLEAD who have completed a mammography since January 1, 2020 to complete a follow-up survey for exploratory aims 2 and 3. The purpose of the T4 survey is to understand how women prefer to learn and receive information about breast cancer risk factors. The survey includes repeated items of perceived risk, demographic characteristics, breast cancer risk factors (i.e., family history, prior biopsy), and new items measuring risk communication, medical mistrust, provider trust, preferences for informed decision making, and social determinants of health (i.e., housing and food insecurity, transportation). Participants will have the option to complete the survey by phone, mail, email, or web-based platform (Zoom). All participants will receive an emailed and/or mailed letter notifying them about changes to the protocol, the purpose of the follow up survey with oral consent, and contact information for a bilingual research coordinator to complete the survey using another modality. The mailed letter will include a paper copy of the survey in English and Spanish with a pre-stamped envelope, and a QR code that participants can scan to complete the follow-up survey on their phone in English or Spanish. Approximately two weeks after the initial mailing/email, eligible participants will receive a reminder letter and email to complete the survey. Participants not responding to the email or mailed letters will receive a follow-up call from a bilingual research coordinator to elicit if the participant received the materials, if they would be interested in completing the survey, preferred mode of completion, and to obtain oral consent. Participants will be contacted up to 4 times (2X by mail/email, 2X by phone) before they will be considered non-responders.

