Aim 1 will compare the percent change in anxiety (STAI) from baseline between the three study groups at one month (T1) and 1 year (T3) following notification. Assuming the percent change may likely range from -100% to +100% (range of 200 percentage points), we conservatively assume a standard deviation of 50 percentage points (range/4) in the percent change measure. We will have 80% power (along with 1.7% type-I error rate) to detect a difference of 9.3 in average percent change between any two of the groups with a two-sample t-test at T2 with 600 per group. At T3, we will have 80% power to detect a difference of 10.6 (466 per group).

The second outcome will be knowledge regarding breast density, measured ordinally as the number correct of 3 key items (range 0-3 correct). This will be tested with pairwise Wilcoxon rank-sum tests, for which the null hypothesis is that the probability of someone answering more items correctly in one group versus another is 0.5 (i.e. equal chance). At T2, with 600 women per group, we will have 80% power (along with 1.7% type-I error rate) to detect a probability of 0.554 or more between any two of the groups. At T3, we will have 80% power to detect a probability of 0.561 (466 per group).

Aim 2 will compare adherence to next routine screening mammogram between the three notification groups. This outcome "adherence to next annual screening" is pertinent to all 2,000 women and will be obtained via EMR. A sample size of 666 in each group will yield 80% power to detect a difference of 9 percentage points between any two of the groups (type-I error rate 1.7%) based on a chi-square test.

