Aim 3 will qualitatively analyze documentation provided by the *promotora* after each patient interaction in the interpersonal study group. Based on the recommendation of Morse,¹¹⁹ we will have ample data from over 600 patient-*promotora* interactions to capture a range of responses. Furthermore, this large sample size will offer the opportunity to qualitatively examine the type of information exchanged for particular subgroups of patients, such as Spanish-speaking only, those receiving notification that they have dense breasts, and those receiving notification that they do NOT have dense breasts. The analysis of Aim 3 qualitative data will provide a rich resource for informing the design of targeted educational materials for specific populations and developing generalizable tools to enhance communication about appropriate risk-based screening for breast cancer.

Data Analysis Plan:

Analytic Approach for Specific Aim 1

This Aim will compare anxiety as well as knowledge gained between breast density notification approaches (usual care, enhanced, interpersonal). Anxiety will be measured using the state anxiety scale within the State Trait Anxiety Inventory (STAI). Items within this scale are rated on a 0 to 3 Likert-type scale and scores are calculated as the sum of the items. The possible scores can range from 0-60, with higher scores indicative of greater anxiety. To adjust for baseline anxiety levels, we will calculate the percent change in anxiety from baseline at each follow-up: $100 * (\text{follow-up anxiety} - \text{baseline anxiety}) / \text{baseline anxiety}$. We hypothesize that there will be less increase in anxiety for the interpersonal group as compared to the enhanced or usual care groups. The percent change will be compared between the three notification study groups with pairwise t-tests at one month as well as at one year following notification. To account for three pairwise comparisons within each time point, P-values less than 0.017 will be considered statistically significant, to preserve an overall type-I error rate of 0.05 within each time point.

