Knowledge regarding breast density will be measured as the number of statements answered correctly as previously described. The number of items answered correctly (range of 0-3) will be compared between the three notification groups with pairwise Wilcoxon-rank-sum tests at one month as well as at 1 year following notification. We assume that baseline knowledge will be similar between the groups due to randomization, and we hypothesize that knowledge will be greater in the interpersonal group as compared to the enhanced or usual care groups. To account for three pairwise comparisons within each time point, P-values less than 0.017 will be considered statistically significant, to preserve an overall type-I error rate of 0.05 within each time point.

Analytic Approach for Specific Aim 2

This Aim will compare adherence to next routine screening mammogram between breast density notification approaches (usual care, enhanced, interpersonal). This information will be obtained from the EMR. The percentage of women who adhere to their next routine screening mammogram will be compared between the three notification groups with pairwise chi-square tests. We hypothesize that women randomized to the interpersonal group will be more likely to adhere to next screening mammogram relative to either the usual care or enhanced study groups. To account for three pairwise comparisons P-values less than 0.017 will be considered statistically significant to preserve an overall type-I error rate of 0.05

Analytic Approach for Specific Aim 3

Framework analysis will be used to understand and analyze the qualitative data provided by the *promotora*. This approach is based in content analysis and allows for *a priori* themes to be identified and categorized as well as *de novo* themes that emerge through inductive analysis. The process begins with familiarization in which the content and range of responses is examined. Next, a thematic framework is generated by identifying key issues, concepts, and themes which will be used to reference the data. We anticipate that issues regarding understanding MBD, supplemental breast screening, and breast cancer risk will arise in the data, but emerging issues will also be captured. Finally, the analytic framework will be applied

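### For anxiety and adherence the flat 0.017 threshold is valid, but a three-group step-down at the same 5% limit would gain power at little cost, by an amount that depends on the effect pattern

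*Combined protocol and SAP*

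**What the plan says.** Analytic Approach for Specific Aim 1 compares percent change in anxiety between the three arms by pairwise t-tests at each of two follow-up times. The rule is: "To account for three pairwise comparisons within each time point, P-values less than 0.017 will be considered statistically significant", with 0.05 as the overall limit per time point. Analytic Approach for Specific Aim 2 compares adherence by pairwise chi-square tests: "To account for three pairwise comparisons P-values less than 0.017 will be considered statistically significant to preserve an overall type-I error rate of 0.05". Neither paragraph has an omnibus gate or a step-down.

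The hypotheses set the interpersonal arm against both others: "We hypothesize that there will be less increase in anxiety for the interpersonal group as compared to the enhanced or usual care groups". Adherence has a parallel hypothesis.

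The Power Statement works pair by pair at 1.7%. For anxiety it claims 80% power for "a difference of 9.3 in average percent change between any two of the groups with a two-sample t-test at T2 with 600 per group", and for 10.6 at T3 with 466 per group. For Aim 2: "A sample size of 666 in each group will yield 80% power to detect a difference of 9 percentage points". It gives no power for showing interpersonal better than both comparators.

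**The concern.** Bonferroni treats the three pairwise hypotheses as if any combination of them could be true. With three means or three proportions that is not so. If usual care equals enhanced and enhanced equals interpersonal, the third equality follows. Hence, if one pairwise null is false, at most one of the other two can be true, and no correction is needed between those two. This is Shaffer's step-down for three groups. The plan gives up this power even though its hypothesis needs two of the three comparisons.

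The gain falls mainly on the harder comparison. The arms are additive: the third is "interpersonal (standard density notification + written educational materials on breast density + verbal interaction with a" promotora, and the enhanced arm already includes the written materials. Interpersonal versus enhanced therefore isolates what the promotora adds. The same additivity makes a graded effect as plausible as two equal arms, so both patterns have to be examined.

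**Working it through.** **Inputs (Power Statement).** SD 50; 600 per group at T2 and 466 at T3; differences 9.3 and 10.6; adherence 666 per group, 9 points. Sidedness is not stated; two-sided tests reproduce the plan's figures, and one-sided tests would give 86–87% for anxiety. The adherence base rate is not given, so a range is assumed.

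**The plan's own figure.** Power ≈ Φ(d / (SD·√(2/n)) − z), with z = √5.696 = 2.387 for two-sided 0.017.
- T2: 9.3 / (50·√(2/600)) = 9.3/2.887 = 3.222; Φ(0.835) = 79.8%.
- T3: 10.6 / (50·√(2/466)) = 10.6/3.276 = 3.236; Φ(0.849) = 80.2%.
- Adherence, 45.5% vs 54.5%: (0.09 − 2.387·√(2·0.25/666)) / √(2·0.455·0.545/666) = 0.0246/0.0273 = 0.902; Φ = 81.6%.

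The stated 80% is reproduced.

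**Rules compared.** Flat: each p < 0.017. Step-down: smallest p against 0.05/3; if it passes, the other two against 0.05. There were 1,000,000 simulated trials per scenario, with pooled t-tests for anxiety and chi-square without continuity correction for adherence. Arm effects are listed in the order usual care, enhanced, interpersonal. I = interpersonal, E = enhanced, U = usual care.

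| Anxiety | Quantity | Flat | Step-down |
|---|---|---|---|
| T2 (0, 0, 9.3) | I vs U, I vs E, each | 79.7% | 86.0% |
| | both | 68.3% | 80.9% |
| | at least one | 91.1% | 91.0% |
| T2 (0, 4.65, 9.3) | I vs U | 79.6% | 80.8% |
| | I vs E | 21.9% | 34.9% |
| | at least one | 80.7% | 81.1% |
| T2 (0, 9.3, 9.3) | I vs U | 79.7% | 85.9% |
| | I vs E (false) | 1.7% | 5.0% |
| T3 (0, 0, 10.6) | each | 80.1% | 86.3% |
| | both | 68.9% | 81.4% |
| T3 (0, 5.3, 10.6) | I vs U | 80.0% | 81.2% |
| | I vs E | 22.1% | 35.1% |

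| Adherence, assumed base rate | Two equal arms, each (flat → step-down) | Graded, I vs U | Graded, I vs E |
|---|---|---|---|
| 45.5% | 81.7% → 87.8% | 81.7% → 83.0% | 23.0% → 36.8% |
| 70% | 91.8% → 95.4% | 91.8% → 92.3% | 32.8% → 48.6% |
| 80% | 98.6% → 99.5% | 98.6% → 98.7% | 51.7% → 68.0% |

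**Error within one family (T2).** No arm differs: 4.5% flat, 4.4% step-down. Two arms equal and the third different: 1.7% flat, 5.0% step-down. For adherence the latter is 4.9–5.2%; the slight excess over 5% comes from the chi-square approximation itself.

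**Error across the three families affected** (anxiety T2, anxiety T3, adherence), assuming independence. Two equal arms in each: 1 − (1 − 0.017)³ ≈ 5% flat, against 1 − (1 − 0.05)³ ≈ 14% step-down. No arm differs: about 13% under either rule.

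**Sample-size equivalent.** At T2, flat 0.017 would need about 695 per group to match the 86%, and about 924 to match the 35%.

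**Intervals.** At T2 with two equal arms, 6.5% of trials per interpersonal comparison (13% for at least one) would be significant by step-down while the Bonferroni interval includes zero. In the graded case it is about 1% for I vs U and 13% for I vs E.

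**Why knowledge is excluded.** The Power Statement says "the null hypothesis is that the probability of someone answering more items correctly in one group versus another is 0.5". That relation is not transitive: two pairs can sit at exactly 0.5 while the third does not. A contrived example on the 0–3 scale shows the consequence. Take score probabilities (0, 1/2, 1/2, 0), (1/3, 0, 2/3, 0) and (0, 2/3, 0, 1/3), with 600 per group. Two pairs are at 0.5 and one at 0.556. In 200,000 trials with tie-corrected Wilcoxon tests, familywise error was 5.5% flat and 10.7% step-down.

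**The case against.** The strongest reply is that nothing here is wrong. The power statement and the analysis use the same 1.7%, and choosing one valid 5% procedure over another is a matter of preference. That is right as far as it goes: this is an efficiency point, not an error.

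The cost also needs a plain statement. The plan does not control error across outcomes and time points, so Bonferroni's slack is its only cushion, and the step-down spends it. The case that matters most is the one where the written materials do all the work (0, 9.3, 9.3): a false claim that the promotora adds something rises from 1.7% to 5%. This stands, though 5% per family is the limit the plan set for itself.

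The benefit is uneven. In the two-equal-arms and graded patterns the chance of at least one interpersonal finding hardly moves, and in the graded one interpersonal versus enhanced still fails about 65% of the time. That also stands.

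Other rules exist. Holm on the two interpersonal contrasts alone (0.025, then 0.05) gives about 88% each and 82% for both at T2 with two equal arms, and 84% for interpersonal versus usual care in the graded pattern. It does so by dropping enhanced versus usual care, which the plan tests. An omnibus test at 5% followed by pairs at 5% gains slightly more (about 87% each, 82% both).

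Replacing 0.017 by 0.05/3 loses a rejection that the flat rule would make in 0.1–0.2% of T2 trials with a real difference, which is negligible.

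Finally, the change may come too late. The T4 section reads "We will identify women enrolled in LLEAD who have completed a mammography since January 1, 2020 to complete a follow-up survey", and the record-review date range runs to 12/01/2022, so T2 and T3 data may already exist. The documents do not say whether outcomes have been seen by arm. This decides whether the change can be made, not whether the reasoning is right.

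**Conclusion.** The point holds as an efficiency recommendation. Flat 0.017 is valid within each family; the step-down keeps the same 5% limit and needs no more participants. At the planned anxiety effects it adds about 6 points per interpersonal comparison and 13 points for showing both when the other two arms are equal. When enhanced lies halfway, it adds about 1 point against usual care and 13 against enhanced. For adherence with two equal arms the gain runs from about 6 points near a 50% base rate to about 1 point at 80% vs 89%.

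The anxiety figures rest on the plan's SD of 50, equal allocation and the planned numbers at T2 and T3. The adherence figures rest on assumed base rates. The 5% guarantee is per outcome and time point only, as it is in the plan.

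**What to change.** In the anxiety paragraph (Specific Aim 1, applied within each time point) and the adherence paragraph (Specific Aim 2), replace the 0.017 sentence with:

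> The smallest of the three pairwise p-values is tested at 0.05/3; if it is significant, the remaining two are each tested at 0.05.

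Leave knowledge at 0.017. Add that confidence intervals are shown at the Bonferroni level, and that a step-down result with p between 0.017 and 0.05 may have an interval that includes zero.

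Make the change only if outcomes have not been seen by arm, and record that with its date. If they have been seen, keep flat 0.017, because relaxing a threshold afterwards would cost more in credibility than it gains in power.

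The cost is one sentence in each of two paragraphs plus the note on intervals, with no new data. The price in error is the rise from 1.7% to about 5% per family when two arms are equal and the third differs, and from about 5% to about 14% over the three families. Knowledge would also follow a different rule from the other two outcomes, which the plan should explain in a line.
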